## **1. INTRODUCTION**

Neuroimmune factors, expressed in neurons and glia, mediate neuroinflammation and modulate a wide range of brain functions, including neuronal activity, endocrine function, and CNS development. A growing body of literature suggests that systemic inflammation leads to neuroinflammation, and alcohol exposure increases both systemic- and neural markers of inflammation. Specifically, chronic alcohol consumption is thought to produce a sustained inflammatory state, such that individuals with alcohol use disorder (AUD) have increased inflammation throughout the brain. Alcohol-induced inflammation has been implicated in chronic alcohol seeking as well as the behavioral and neurotoxic effects of alcohol. In rodents, lipopolysaccharide (LPS)-induced inflammation produces prolonged increases in alcohol consumption, and knocking out immune signaling genes attenuates alcohol preference and self-administration. Thus, elucidating the role of inflammation in AUD has significant implications, including opportunities for the development of novel and potentially more effective therapeutics for AUD.

The proposed study consists of a randomized, double-blind, placebo-controlled trial of low dose endotoxin. The low dose endotoxin challenge induces a transient systemic inflammatory response with normalization of cytokine levels within hours. This “phasic” inflammation is distinct from chronic (“tonic”) levels of inflammation that may be present with AUD.

## **2. BACKGROUND AND SIGNIFICANCE**

### **2.1. Inflammatory signaling appears to be a key component of alcohol use disorder.**

Molecular and behavioral studies suggest a central role for the innate immune system in mediating the acute and chronic effects of alcohol and generally support an inflammatory hypothesis of alcohol use disorder. Neurotrophins, including glial (GDNF) and brain derived neurotrophic factor (BDNF), are essential for synaptic plasticity, neuron survival, and basic cell signaling, including midbrain dopamine transmission. In rodent models of AUD, reductions in GDNF and BDNF expression underlie dysfunctional striatal dopamine signaling, increased motivation to consume alcohol, and heightened alcohol reward. Conversely, increases in GDNF and BDNF signaling restores mesolimbic dopamine function, reduces alcohol self-administration, and attenuates relapse to alcohol seeking. In preclinical studies, induction of inflammation produces prolonged increases in alcohol consumption, and knocking out inflammatory signaling genes attenuates alcohol preference and self-administration.

Proinflammatory signaling also mediates acute alcohol-induced motor impairment, and chronic alcohol exposure produces long-lasting increases in systemic inflammation, which in turn is associated with sustained cognitive and behavioral impairment and brain damage. Furthermore, inflammation is thought to increase vulnerability to stress-induced drug seeking and relapse.

It is hypothesized that chronic alcohol consumption produces a sustained inflammatory state, and in turn, this alcohol-induced neuroinflammation contributes to the behavioral and neurotoxic effects of alcohol. Individuals with AUD are thought to have increased neuroinflammation throughout the brain, and elevated peripheral levels of proinflammatory cytokines have been

proposed as a biomarker for AUD. Nevertheless, there are contrasting findings such that a recent imaging study reported that individuals with AUD exhibit less activated microglia in the brain and blunted peripheral proinflammatory response than controls. In sum, the role of inflammation in AUD remains opaque, particularly in human/clinical studies.

## **2.2. The literature on inflammatory signaling and AUD is overwhelmingly preclinical and translation to human clinical samples is sorely needed.**

To date, the vast majority of the research implicating alcohol and inflammation has been preclinical. Human studies, however, have recently shown a positive correlation between serum levels of inflammatory cytokines and alcohol craving. While these associations are intriguing, it is crucial for the field to progress from correlational to experimental models that can effectively probe the role of neuroinflammation in AUD phenotypes in humans. This is particularly relevant given recent evidence that genomic responses to inflammation and inflammatory disease in mouse models cannot be extrapolated to the human condition, which “supports higher priority to focus on the more complex human conditions rather than rely on mouse models to study human inflammatory diseases.” To that end, we propose to conduct an inflammatory challenge in a sample of non-treatment-seeking heavy drinkers and a comparison sample of light drinkers to examine the effects of systemic increases in inflammation on cue-induced craving for alcohol in the laboratory. Such endotoxin-induced increases in systemic inflammation are reported to induce neuroinflammation with glial activation in humans. Specifically, we propose to experimentally provoke an inflammatory response using low dose endotoxin derived from *E. coli* (*E. coli* group O:113:BB-IND 12948 to MRI) and delivered intravenously. This reference endotoxin provided by the NIH Clinical Center has demonstrated safety and has been successfully administered at UCLA by the investigative team in studies of inflammation, socioemotional processes, and depression. The proposed study will leverage these resources for a safe, effective, and well-tolerated inflammatory challenge in order to experimentally probe the role of inflammation in alcohol craving among non-treatment-seeking heavy drinkers. The scientific premise of this proposal is that if inflammation plays a causal role in inducing alcohol craving, heavy drinkers will experience greater cue-induced alcohol craving following an inflammatory challenge (via endotoxin) as compared to those given a placebo challenge. In addition to a human study showing a positive correlation between serum levels of cytokines and alcohol craving, a host of preclinical studies have shown that while endotoxin administration reduces effort, it actually boosts preference for high rewards, thus advancing craving as a plausible reward-based outcome for this study.

## **2.3. Significance of the proposed project hinges on the premise that while evidence is accumulating that the innate immune system and inflammation contribute to AUD, the evidence is largely preclinical and translation to human clinical samples is necessary.**

The findings in humans have been mostly correlational while experimental approaches that can establish a causal link between inflammation and AUD phenotypes is lacking. The proposed study fills an important gap in the literature by examining the role of inflammation in alcohol craving in a clinical sample of non-treatment-seeking heavy drinkers and light drinking healthy controls. The successful completion of the proposed study will advance the field of alcoholism by experimentally probing the role of neuroinflammation in alcohol craving, a translational phenotype for AUD. Results from this study will inform an R01 application in which the combination of inflammatory challenge and alcohol cue-reactivity can be used in medications

[figure not shown]
development applied to novel neuroimmune modulators with therapeutic potential for AUD. Notably, this approach has been successful in the psychoneuroimmunology (PNI) field.

## 2.5. Cue-reactivity represents an important translational phenotype for alcoholism.

[name] has an active research program using experimental approaches to elucidating AUD etiology and treatment development. [name] laboratory has ample expertise applying cue-reactivity methods to AUD. For example, in a recent publication, [name] and her team examined craving for alcohol during an alcohol administration (i.e., comparing I.V. alcohol vs. placebo control) as well as during a cue-reactivity paradigm (i.e., comparing water cue vs. alcohol cue) in individuals with AUD. As shown in **Figure 1**, there is a main effect of alcohol administration (vs. placebo) in eliciting craving as well as a main effect of alcohol cue (versus water cue). The cue-reactivity paradigm proposed herein is consistent with those successfully implemented in [name] laboratory,

[figure not shown]
including studies of cue-reactivity among individuals with AUD. Further, we have demonstrated the safety of these procedures, by evaluating drinking behavior following study participation. More recently, we have become interested in comparing treatment-seekers to non-treatment seekers in cue-induced craving. Preliminary analyses with a sample of 29 individuals with moderate-to-severe AUD showed no significant differences in cue-reactivity between treatment-seekers (N=15) and non-treatment seekers (N=14) ( $F(2,28)=0.42, p= .66$ ) (see **Figure 2**).

## 2.6. Endotoxin provides a safe and reliable probe of inflammatory response.

Drs. [name] and [name] have expertise in PNI including a host of studies using endotoxin to provoke an inflammatory response. Specifically, using low dose endotoxin derived from *E. coli* (*E. coli* group O:113:BB-IND 12948 to MRI) and delivered intravenously, Drs. [name] and [name] demonstrated reliable increases in plasma levels of proinflammatory cytokines [i.e., Interleukin-6 (IL-6) and tumor necrosis factor- $\alpha$  (TNF-  $\alpha$ )] which peak at 2 hours post infusion (see **Figure 3**). This reference endotoxin provided by the NIH Clinical Center has demonstrated

safety and has been successfully administered at UCLA by the investigative team in studies of inflammation and depression. The proposed study will leverage these resources for a safe, effective, and well-tolerated inflammatory challenge in order to experimentally probe the role of inflammation in alcohol craving among non-treatment seeking heavy drinkers and light drinking controls.

## 2.7. Acute inflammation induces neural changes detectable by neuroimaging.

Translating the role of inflammation in AUD from preclinical animal models to clinical populations has been slow. Because it is the only non-invasive technique to assay the living brain, neuroimaging represents an important tool to translate findings from preclinical studies to individuals with addictive disorders [39]. Neuroimaging provides objective quantifications of brain activation, beyond what can be gathered from subjective self-report data alone [40]. Critically, functional magnetic resonance imaging (fMRI) paradigms have been used to detect alterations in the neural signal induced by acute inflammation [13, 14, 41, 42]. In healthy individuals, acute inflammation induced by endotoxin attenuated ventral striatal activation to anticipation of a monetary reward, which was further associated with increases in depressed mood [14]. Acute inflammation enhanced neural activation to both positive and negative social feedback, such that endotoxin increased amygdala activation to negative social feedback and increased reward-related activation (ventral striatum, ventromedial prefrontal cortex) to positive social feedback [13]. These studies emphasize the complexities of the role of acute inflammation in reward processing, such that the neural response to positive social feedback is potentiated whereas it is attenuated to monetary reward.

Importantly, no studies have yet investigated the effect of acute inflammation on the neural response to alcohol cues in AUD or other addictive disorders. fMRI alcohol cue-reactivity paradigms have been commonly used to evaluate if pharmacological AUD treatments alter brain activation in circuitry associated with reward processing [43, 44], and as such are sensitive to biological changes in the body as would be present in an inflammatory state. Therefore, the proposed study will fill an important gap in the literature by examining the role of acute inflammation on the neural substrates of alcohol cue reactivity in a clinical sample of non-treatment-seeking heavy drinkers and light drinking healthy controls. The successful completion of the proposed study will advance the field of alcoholism by experimentally probing the role of neuroinflammation in alcohol craving, a translational phenotype for AUD. Results from this study will inform an R01 application in which the combination of inflammatory challenge and alcohol

cue-reactivity can be used in medications development applied to novel neuroimmune modulators with therapeutic potential for AUD [9, 45]. Notably, this approach has been successful in the psychoneuroimmunology (PNI) field [46, 47].

### 3. STUDY OBJECTIVES

#### 3.1. Primary Aims

Primary Aim #1: To test whether low dose endotoxin (0.8 ng/kg of body weight) will increase cue-induced craving for alcohol in non-treatment-seeking heavy drinkers, as compared to placebo and as compared to light drinking controls. Based on the correlational findings of a positive association between proinflammatory cytokines and alcohol craving (8, 9), as well as preclinical studies (16-18), we hypothesize that endotoxin will produce greater cue-induced alcohol craving than placebo infusion.

Primary Aim #2: To test whether low dose endotoxin (0.8 ng/kg of body weight) will increase depressed mood as compared to placebo. Based on recent work by our Co-Is (13), we hypothesize that endotoxin will produce greater increases in depressed mood than placebo infusion.

#### 3.2. Exploratory Aims

Exploratory Aim #1: To test associations between plasma levels of proinflammatory cytokines (IL-6 and TNF-  $\alpha$ ), depressed mood, and alcohol craving during the challenge.

Exploratory Aim #2: To examine sex differences in responses to the endotoxin challenge.

Exploratory Aim #3: To determine the effect of low dose endotoxin (0.8 ng/kg of body weight) on neural alcohol cue-reactivity.

Exploratory Aim #4: To determine the effect of low dose endotoxin (0.8 ng/kg of body weight) on reward responsiveness.

### 4. STUDY DESIGN

#### 4.1. Design Overview

The study design consists of a randomized, double-blind, placebo-controlled trial of low dose endotoxin. The low dose endotoxin challenge induces a transient systemic inflammatory response with normalization of cytokine levels within hours. This “phasic” inflammation is distinct from chronic (“tonic”) levels of inflammation that may be present with AUD. A total of 38 non-treatment seeking heavy drinking men and women and 38 light drinking healthy controls will participate in the study. Recruitment will be monitored to ensure the two groups are matched by gender. Eligible participants will be randomly assigned to receive a single I.V. infusion of either low dose endotoxin (0.8 ng/kg of body weight) or placebo (same volume of 0.9% saline solution) at the UCLA Outpatient Clinical and Translational Research Center (CTRC). All participants will complete an alcohol cue-exposure paradigm 2 hours post infusion, which is the time of expected peak cytokine response (13, 14). Participants will complete the fMRI alcohol cue reactivity paradigm 3 hours post infusion. Plasma levels of proinflammatory cytokines [i.e.,

Interleukin-6 (IL-6) and tumor necrosis factor- $\alpha$  (TNF-  $\alpha$ ), mood, reward reactivity, and alcohol craving, will be assessed at baseline and then hourly for four hours post infusion.

## 5. STUDY PROCEDURES

### 5.1. Recruitment of Subjects

Participants will be recruited from the community through online and newspaper advertisements. Campaigns in local buses and print publications (e.g., LA Weekly) will also be implemented. Targeted recruitment will also take place through a lab database of previous study participants who agreed to be contacted for future studies.

### 5.2. Eligibility Criteria

#### 5.2.1. Inclusion Criteria

To be included in the study, participants must:

- (1) Be between the ages of 21 and 45
- (2) Be non-treatment seeking for AUD
- (3) Have had at least one alcoholic beverage in the last 30 days
- (4) FOR HEAVY DRINKERS: Alcohol Use Disorder Identification Test (AUDIT) score between 8 – 15; FOR LIGHT DRINKERS: AUDIT score < 4
- (5) FOR HEAVY DRINKERS: Report drinking at binge levels at least 1 time in the past month (5+ drinks/day for men, 4+ drinks/day for women); FOR LIGHT DRINKERS: report no occasions of binge drinking in the past month

#### 5.2.2. Exclusion Criteria

To be included in the study, participants must not:

- (1) Have a current (last 12 months) DSM-5 diagnosis of substance use disorder for any psychoactive substances other than alcohol and nicotine
- (2) Have a lifetime DSM-5 diagnosis of schizophrenia, bipolar disorder, or any psychotic disorder
- (3) Have current moderate to severe depression as indicated by a score of  $\geq 21$  on the Beck Depression Inventory – II (BDI-II)
- (4) Have current suicidal ideation or lifetime history of suicide attempt as reported on the Columbia-Suicide Severity Rating Scale (C-SSRS)
- (5) Have a positive urine screen for drugs other than cannabis;
- (6) Have clinically significant alcohol withdrawal symptoms as indicated by a score  $\geq 8$  on the Clinical Institute Withdrawal Assessment for Alcohol-Revised (CIWA-R)
- (7) Have an intense fear of needles or have had any adverse reactions to needle puncture
- (8) Be pregnant, nursing, or planning to become pregnant while taking part in the study; and must agree to one of the following methods of birth control (if female), unless she or partner are surgically sterile:
  - Oral contraceptives
  - Contraceptive sponge
  - Patch
  - Double barrier
  - Intrauterine contraceptive device

- Etonogestrel implant
- Medroxyprogesterone acetate contraceptive injection
- Complete abstinence from sexual intercourse
- Hormonal vaginal contraceptive ring

(9) Have a medical condition that may interfere with safe study participation (e.g., unstable cardiac, renal, or liver disease, uncontrolled hypertension or diabetes, autoimmune or inflammatory disease)

(10) Have clinically significant abnormal EKG

(11) Have > Grade 2 laboratory abnormalities, based on FDA Guidance Document “Toxicity Grading Scale for Healthy Adult and Adolescent Volunteers Enrolled in Preventive Vaccine Clinical Trials”

(12) Have any other circumstances that, in the opinion of the investigators, compromises participant safety

(13) Have non-removable ferromagnetic objects in body

(14) Have claustrophobia

(15) Have serious head injury or prolonged period of unconsciousness (>30 minutes)

#### 5.2.3. Exclusion Criteria for Inflammatory Challenge Visits

To participate in the inflammatory challenge, participants must not show any of the following upon arrival to the inflammatory challenge study visit:

- (a) BrAC > 0.000 g/dl
- (b) clinical withdrawal (CIWA-R) score  $\geq 8$
- (c) blood pressure  $\leq 90/60$  or  $\geq 160/120$
- (d) resting pulse  $\leq 50$  beats/minute or  $> 100$  beats/minute
- (e) temperature  $\geq 99.5^{\circ}\text{F}$
- (f) recent (past 2 weeks) acute illness or vaccination
- (g) score of 10+ on Physical Sickness Symptoms Assessment

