## 5.4. Experimental Visit

### 5.4.1. Randomization

Participants who are eligible after the physical exam will be randomized to an experimental condition (i.e., endotoxin vs. placebo) within an appropriate amount of time based on study physician discretion. Urn randomization will be used to balance the two groups by gender and BDI-II severity. The UCLA Research Pharmacy will manage the blind. The two treatment conditions will not be different in appearance or method of administration. However, it is

possible that participants undergoing the endotoxin challenge who feel very symptomatic may suspect that they are in the active condition. For this reason, we have decided to exclude individuals who experience severe sickness symptoms as described below (which is expected to be less than 5% of the sample). If participants are withdrawn from the study due to sickness symptoms, their data will be retained for the purposes of reporting adverse events and safety data during the trial. Additional subjects will be recruited to replace the withdrawn individuals.

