#### 5.4.2. Inflammatory Challenge (endotoxin or matched placebo)

Upon arrival to the CTRC, eligibility for the inflammatory challenge will be reviewed to ensure that none of the exclusion criteria have been met as described above. A nurse, who will be blind to the condition, will insert a catheter with a heparin lock into the non-dominant forearm for drug administration and hourly blood draws. Each participant will be randomly assigned to receive either low-dose endotoxin (0.8 ng/kg of body weight administered) or placebo (same volume of 0.9% saline), which will be administered by the nurse as an intravenous bolus. The endotoxin will be derived from *Escherichia coli* (*E. Coli* group O:113: BB-IND 12948 to M.R.I) and will be provided by the National Institutes of Health Clinical Center as a reference endotoxin for studies of experimental inflammation in humans. Participants will complete assessments as outlined below at baseline and every hour for 4 hours post-infusion. One standard meal and one snack will be provided by the CTRC to each participant during the experimental visit, and participants will be provided oral hydration throughout the visit. At the end of the experimental period, participants will have the catheter removed and will be discharged with instructions to abstain from consuming alcohol for 24 hours after discharge. A follow-up phone call will be conducted the day after the inflammatory challenge and again 1-2 weeks later to assess for any adverse events.

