#### **6.2.31. Physical Sickness Symptoms Assessment**

Symptoms of physical sickness will be self-reported during each experimental visit on a scale from 0 (symptom not present) to 4 (very severe) at multiple time points (baseline, T1, T2, T3 and T4). At the baseline assessment, participants must have a total score below 10 in order to move forward with the experimental challenge. Scores of 10 or above will result in the visit being rescheduled when the participant is feeling better. Participants who rate any symptom as a '4' at the T1 – T4 assessment will be withdrawn from the study prior to the cue-reactivity paradigm. Research staff will contact the study physician and/or nurse practitioner on call to manage any severe sickness symptoms reported during the experimental session.

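### The baseline sickness gate tests only the total score, so a participant already reporting one or two very severe symptoms can be infused

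*Combined protocol and SAP*

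**What the plan says.** All references are to the combined protocol and SAP.

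- **Gate on arrival.** Section 5.2.3(g) excludes from the challenge anyone with a "score of 10+ on Physical Sickness Symptoms Assessment". Section 6.2.31 states the same limit: "At the baseline assessment, participants must have a total score below 10 in order to move forward with the experimental challenge". Failing it delays the visit rather than ending participation: "Scores of 10 or above will result in the visit being rescheduled when the participant is feeling better".
- **Scale.** Section 6.2.31 scores each symptom from 0 (absent) to 4 (very severe) at baseline and at T1 to T4.
- **Rule after infusion.** The same section changes the criterion from the total to the single item. Anyone who rates any symptom 4 at the T1 to T4 "assessment will be withdrawn from the study prior to the cue-reactivity paradigm". The rule makes no reference to the baseline rating.
- **Consequence.** Under section 5.4.1, data from people withdrawn for sickness are retained for adverse-event and safety reporting, and "Additional subjects will be recruited to replace the withdrawn individuals". The reason given is that it is "possible that participants undergoing the endotoxin challenge who feel very symptomatic may suspect that they are in the active condition".
- **Clinical back-up.** Section 6.2.31 adds: "Research staff will contact the study physician and/or nurse practitioner on call to manage any severe sickness symptoms reported during the experimental session".

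**The concern.** The protocol treats a single rating of 4 as decisive once the infusion has been given, but attaches no defined consequence to the same rating just before it. Baseline is the one moment when acting on it costs almost nothing, because the infusion has not been given and rescheduling is already available.

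Two practical matters are at stake. The first is participant safety: an inflammatory agent may be given to someone who already reports a very severe symptom. The second is a wasted exposure: if the rating is still 4 at T1, the participant is withdrawn before the T2 cue session and contributes nothing to the efficacy analysis, and someone else must be enrolled and infused.

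**Working it through.** **Inputs.** The item range is 0 to 4 (6.2.31). The gate is a total below 10 to proceed (6.2.31), with 10 or more excluded (5.2.3(g)). The withdrawal rule is any item equal to 4 at T1 to T4 (6.2.31). Replacement is in 5.4.1. The target is 76 completers (8.1).

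**Step 1: the gate itself.** The two statements agree. Excluding 10 or more and requiring a total below 10 both make 9 the highest passing total.

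**Step 2: how many items at 4 fit under the gate.** With k items rated 4, the minimum total is 4k, and the points left for all other items are 9 − 4k.

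| Items at 4 (k) | Minimum total (4k) | Points left (9 − 4k) | Passes T0 gate? | Would meet the T1–T4 withdrawal rule? |
|---|---|---|---|---|
| 0 | 0 | 9 | Yes | No |
| 1 | 4 | 5 | Yes (total 4 to 9) | Yes |
| 2 | 8 | 1 | Yes (total 8 to 9) | Yes |
| 3 | 12 | none | No | Yes |

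The gap is exactly the rows k = 1 and k = 2. Two items at 4 pass only if everything else adds up to 1 point or less.

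**Step 3: whether another provision sets an item limit at T0.**

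- Section 5.2.3(a) to (f) covers breath alcohol, withdrawal score, blood pressure, pulse, temperature, and illness or vaccination in the preceding two weeks. These may stop some of these participants, but none reads a single symptom rating.
- Section 5.4.2 provides that "eligibility for the inflammatory challenge will be reviewed to ensure that none of the exclusion criteria have been met as described above". It refers back to the same list and adds no threshold.
- Section 6.2.25 places an eligibility checklist at the start of the visit but states no limit of its own.
- The toxicity grading checklist is scheduled at T0 (6.1), but 6.2.43 ties its eligibility use to laboratory results.
- The questionnaire in 6.2.24 collects recent illness, vaccination and medication, with no cut-off.
- Section 5.2.2 item 12 gives the investigators general discretion on safety.
- The on-call sentence in 6.2.31 tells staff to have severe symptoms managed. It does not tell them to withhold the infusion.

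None of these sets an item-level limit on this scale.

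**Step 4: cost per case.** If the 4 has resolved by T1 and does not recur, there is no withdrawal and no extra enrolment. If it persists, there is one withdrawal and one replacement: 76 + 1 = 77 people infused to reach 76 completers. For scale, the protocol expects exclusions for severe sickness of any origin to stay under 5% of the sample, and 0.05 × 76 = 3.8, so fewer than four people. It gives no figure for ratings of 4 at baseline.

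**Step 5: effect of an added item limit.** Rows k = 1 and k = 2 would fail at T0 and be rescheduled. Row k = 3 fails already. The planned number of completers does not change.

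**The case against.** The strongest reply is that gating on a total is a legitimate choice. The T0 gate asks whether the overall sickness burden is low enough to proceed, while the T1 to T4 rule deals with very symptomatic participants after infusion. They do different jobs and need not use the same measure. **This stands.** A reader might infer that the two rules contradict each other. They do not, because the later rule does not apply at T0.

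The second reply is that clinical checks largely cover the case. Baseline is part of the experimental visit, so the on-call sentence in 6.2.31 most naturally covers a rating of 4 at T0. With investigator discretion and the other arrival criteria, a very ill participant would often be stopped. **This stands as to likelihood.** It does not close the gap, since it depends on someone noticing one item inside an acceptable total and then deciding to withhold the infusion.

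The third reply concerns the reason for withdrawal. A reader might infer that a participant whose 4 persists is removed for a symptom that predates the infusion, outside the rationale in 5.4.1. The documents do not support that. Someone still at the top of the scale after infusion may well suspect the active arm, which is the concern that 5.4.1 describes. Because 4 is the maximum, the rating also cannot show whether endotoxin made the symptom worse, and a change-from-baseline condition would not help. **This stands**, and it is why the T1 to T4 rule should be left alone.

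Finally, neither the symptom list nor the contents of the eligibility checklist is reproduced in the documents. Some items might be complaints for which rescheduling is unnecessary. **This stands as a limit** on how much the gap matters in practice, though not on the arithmetic.

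**Conclusion.** The point holds as a small gap in the written entry rule. One or two symptoms rated very severe at T0 satisfy 5.2.3(g) and 6.2.31, so the participant can be infused while already at the level that triggers withdrawal an hour later.

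The size is at most one avoidable exposure, one lost visit and one extra enrolment for each case in which the 4 persists, and no withdrawal where it resolves and does not recur. The frequency cannot be computed from the documents and is probably low. The conclusion assumes that the unseen eligibility checklist carries no item limit beyond the criteria in 5.2.3.

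A reader might infer bias or a loss of power. Neither follows. The T0 rating is made before infusion and should be similar in the two arms under randomization, and replacement preserves the 76 completers. No misreporting of adverse events is implied either. Severity: optional.

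**What to change.** In 5.2.3(g), in 6.2.31 and on the eligibility checklist, require at T0 **both** a total below 10 **and** no single item rated 4. If either condition fails, reschedule the visit by the route that 6.2.31 already provides for totals of 10 or above. Leave the T1 to T4 withdrawal rule, the sample size and the analysis unchanged.

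The cost is one line in each of the three places and an occasional rescheduled visit.
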